**Document History – Changes compared to previous final version of SAP**

Date	Time point	Reason for update	Outcome for update	Section and title impacted (Current)
17-May-2017	Prior to DB lock	Creation of final version	N/A - First version	NA
25-Mar-2019	Prior to DB lock	Amended to be aligned with protocol amendment	N/A	Section 1.1, 1.2, 2.1, 2.2, 2.3, 2.4, 2.5, 2.6, 2.7, 2.14, 3, 5 and 6
27-Jul-2019	Prior to DB lock	Amended based on comments on dry run	Remove some baseline characteristics; Correct significance level of confidence intervals; Add dose response analysis of ESSPRI dryness, fatigue, and pain subscores; [REDACTED] Add CTC grade for Lymphocytes; Add steroid conversion table.	Section 2.3, 2.5.1, 2.6.4, 2.10, 5.3 and 5.6

## List of abbreviations

AE	Adverse event
ATC	Anatomical Therapeutic Classification
AUC	Area Under the Curve
bid	bis in diem/twice a day
CSR	Clinical Study report
CTC	Common Toxicity Criteria
CTCAE	Common Terminology Criteria for Adverse Events
DMC	Data Monitoring Committee
DMARD	Disease modifying anti-rheumatic drug
FAS	Full Analysis Set
eCRF	Electronic Case Report Form
IVR	Interactive Voice Response
IWR	Interactive Web Response
MedDRA	Medical Dictionary for Drug Regulatory Affairs
NCI	National Cancer Institute
o.d.	Once Daily
OS	Overall Survival
PFS	Progression-Free Survival
PK	Pharmacokinetics
PPS	Per-Protocol Set
PRO	Patient-reported Outcomes
qd	Qua'que di'e / once a day
QoL	Quality of Life
RAP	Report and Analysis Process
RECIST	Response Evaluation Criteria in Solid Tumors
SAP	Statistical Analysis Plan
SOC	System Organ Class
TFLs	Tables, Figures, Listings
WHO	World Health Organization

## 1 Introduction

The purpose of this Statistical Analysis Plan (SAP) is to describe the implementation of the statistical analysis planned in the data analysis section 9 of the study protocol.

This SAP will be used in executing the final CSR for this study. It can also be used to execute primary efficacy analysis when all patients complete Week 24.

### 1.1 Study design

This is a randomized, double-blind, placebo-controlled, multicenter, parallel-group trial in approximately 180 patients with active pSS. The study is divided into 4 study periods:

**Period 1:** A screening period of 4 weeks to assess patient eligibility. Patients can be re-screened only once and no study-related re-screening procedure should be performed prior to written re-consent by the patient.

**Period 2:** At baseline, eligible patients will be randomized to one of three VAY736 dose arms (VAY736 5 mg, 50 mg or 300 mg s.c.) or a placebo arm. Blinded study drug will be administered every four weeks for a 24-week period. Approximately 45 patients will be randomized per treatment group. [REDACTED], randomization will be stratified by:

- baseline ESSDAI score (<10 or  $\geq 10$  based on weighted scores)

[REDACTED]

The primary endpoint will be assessed at the end of period 2 (week 24).

[figure not shown]
Treatment assignment in period 2 will remain double blinded until the end of period 3.

**Period 3:** After week 24 assessments, patients in the VAY736 300 mg arm will be re-randomized in a 1:1 ratio to either continue VAY736 300 mg s.c. every four weeks or switch to [REDACTED] placebo up to week 52. Patients who received placebo during period 2 will be switched to VAY736 150 mg s.c every four weeks up to week 52. Patients who received 5 mg and 50 mg s.c. in period 2 will proceed directly to period 4. Treatment assignment in period 3 will remain double blinded until the end of the study period.

**Period 4:** The safety follow-up period lasts for a minimum of 20 weeks from last dose administration of VAY736, or longer (with reduced visit frequency) [REDACTED] whichever occurs first ([Figure 1-1](#)) ([van Vollenhoven 2012](#); [Emery 2014](#), [Genovese 2008](#)).

Patients who have not yet recovered their B-cell counts two years after last VAY736 dosing, will be discharged from the study and undergo their End of Study (EoS) visit. Patients who will be treated with another immunmodulatory or immunsuppressive treatment (e.g. azathioprine, cyclophosphamide, high dose glucocorticosteroids) after completion of the minimum 20 week safety follow-up period are excluded from further safety follow-up.

The primary efficacy analysis will be performed when all patients have completed the week 24 study visit.

**Figure 1-1** Study design

[figure not shown]
\*Only patients in the period 2 VAY736 300 mg arm will be eligible for period 3 re-randomization. Patients who were randomized to Pbo in period 2 will receive double blind VAY736 150mg s.c. every 4 weeks, but will not be re-randomized in period 3. All other patients will proceed directly from period 2 to period 4 (Safety Follow-Up period).

## 1.2 Study objectives and endpoints

**Table 1-2** Objectives and related endpoints

Objective	Endpoint
Primary	
To demonstrate a dose response of VAY736 defined as change in ESSDAI from baseline at 24 weeks	Change in ESSDAI score from baseline over 24 weeks as compared to placebo
Secondary	
To assess a dose response of VAY736 in the change from baseline of ESSPRI at 24 weeks	Change in ESSPRI score from baseline over 24 weeks as compared to placebo
To assess a dose response of VAY736 in the change from baseline of the Functional Assessment of Chronic Illness Therapy-Fatigue Scale (FACIT-F) at 24 weeks	Change in FACIT-F from baseline over 24 weeks as compared to placebo
To assess a dose response of VAY736 in the change from baseline of SF-36 at 24 weeks	Change in SF-36 physical component (PCS) and mental component (MCS) from baseline over 24 weeks as compared to placebo

Objective	Endpoint
To assess changes from baseline in PhGA of the patient's overall disease activity at week 24	Change from baseline in PhGA of patient's overall disease activity (recorded by VAS) over 24 weeks as compared to placebo
To assess change from baseline of ESSDAI, ESSPRI, PhGA, PaGA, FACIT-F, SF-36 at weeks 4, 8, 12 and 16.	Change in ESSDAI, ESSPRI, PhGA, PaGA, FACIT-F, and SF-36 from baseline at weeks 4, 8, 12, and 16 as compared to placebo
To evaluate the effects of VAY736 on salivary gland function at 24 weeks	Change from baseline in salivary flow rate (unstimulated and stimulated) at 24 weeks as compared to placebo
[REDACTED]	
To assess safety and tolerability of VAY736	AEs, SAEs, and routine safety laboratory tests
To assess immunogenicity (IG) of VAY736	Serum anti-VAY736 antibodies (ADA assay) during treatment and follow up period
To assess PK of VAY736 after multiple s.c. doses	Monthly and follow up PK measurements at the four dose levels
[REDACTED]	

## **2 Statistical methods**

### **2.1 Data analysis general information**

The analyses will be performed in SAS 9.3 or later (SAS Institute, Cary NC).

Descriptive statistics on continuous data will include mean, standard deviation, median, 25th and 75th percentiles, minimum and maximum, while categorical data will be summarized as frequencies and percentages.

Inferential modeling for primary and key secondary variables will include geographic region, and stratification factor baseline ESSDAI score <10 or  $\geq 10$ .

**Table 2-1 Geographic Regions**

Region	Countries
1	Argentina, Spain, Chile, France, Portugal, Italy
2	US, UK
3	Austria, Germany, Israel, Belgium, Netherlands
4	Romania, Russia, Hungary, Poland
5	Japan, Taiwan

## 2.1.1 General definitions

### Study treatment

The following grouping scheme / data selection will be used for reporting of safety summary:

Grouping Scheme 1 (short term summary, up to 24 weeks): only data on or before the end of treatment (defined below) in period 2 will be tabulated. The treatment used will be according to the treatment groups initially received:

Placebo  
VAY736 5 mg  
VAY736 50 mg  
VAY736 300 mg  
Any VAY736

Grouping Scheme 2 (long term summary, all study periods):

VAY736 5 mg  
VAY736 50 mg  
VAY736 150 mg  
VAY736 300 mg 24 Weeks (this group includes patients receiving VAY736 300 mg and stopping treatment in period 2, as well as those receiving placebo in period 3)  
VAY736 300 mg 52 Weeks  
Any VAY736 300 mg  
Any VAY736

### Study day

Day 1 is defined as the date of first dose of study drug (VAY736 or Placebo). Study day is defined as the number of days since the date of first dose of study treatment (Day 1).

Therefore, for a particular date, study day will be calculated as follows:

- For dates on or after the date of first administration of study treatment,  
Study day = Assessment date – Date of first dose of study treatment + 1;
- For dates prior to the date of first administration of study treatment,  
Study day = Assessment date – Date of first dose of study treatment.

### Baseline

The baseline value is defined as the last assessment prior to first dose administration. In case the scheduled baseline assessment value is missing, the screening value will be used instead.

### Treatment-emergent adverse event

A treatment-emergent adverse event (AE) is defined as any adverse event started after the first dose of study treatment or events present prior to the first dose of study treatment but increased in severity based on preferred term (PT).

### **End of Treatment Date (EoT)**

The end of treatment date is the date of EoT disposition on CRF page for patients who complete the study treatment(s) as per protocol, or the date of the last dose plus 27 days if patients early discontinue the treatment. Therefore, the end of treatment date (EoT) in period 2 is defined as below:

- 1) patients who complete period 2 treatment and enter period 4 directly: EoT = the date of period 2 disposition on CRF page
- 2) patients entering period 3: EoT = the date of the first dose in period 3
- 3) patients early discontinue the treatment in Period 2: EoT = the date of the last dose in period 2 plus 27 days .

The end of treatment date (EoT) in period 3 is defined as below:

- 1) patients who complete period 3 treatment: EoT = the date of period 3 disposition on CRF page
- 2) patients early discontinue the treatment in Period 3: EoT = the date of the last dose in period 3 plus 27 days .

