3.6 Risks and benefits

Initially, patients have a 75% chance to be treated with a potentially efficacious treatment for a chronic disease with possible long term outcomes including serious disabilities. Patients who receive placebo up to week 24 in period 2 will receive active treatment with VAY736 in period 3. Patients who are on placebo in period 2 and are being discontinued prior to week 24 for any reason will not be eligible to receive active treatment in period 3. The study is designed to limit exposure to placebo. However, for the 25% of patients who will receive placebo in period 2, no other approved systemic therapy exists, and thus i) certain background therapy is allowed during the trial and ii) in period 3, the opportunity of receiving active treatment.

As VAY736 is a systemic immunosuppressive treatment, the study population will be limited to include patients with moderate-to-severe pSS who are most likely to benefit from such a therapy. Based on a risk/benefit evaluation it was concluded that very severely ill patients with high steroid requirements (>10 mg/day prednisone or equivalent) or in need of immunosuppressive treatments such as cyclophosphamide, should not be included in this first multiple dose study of VAY736 in pSS. Hence, these medications are disallowed to be used concomitantly ([Table 5-1](#)).

Acute injection reactions: First-dose mild-to-moderate injection reactions were observed in the phase 1/2a studies in a substantial subset of patients.

Therefore,

[REDACTED] a mandatory pre-medication with i.v. methylprednisolone (with or without additional antihistamine and/or paracetamol medication at the discretion of the investigator) prior to the first VAY736 dose will be administered in the current trial.

Infections: At the time of protocol amendment, no SAEs related to infections have been observed in VAY736 exposed patients (during/after VAY736 exposure) in the ongoing or completed VAY736 clinical trials. An increase in mild-to-moderate upper respiratory tract infections compared to placebo has been associated with use of VAY736.

[REDACTED]

Neutropenia:

Late onset neutropenia (LON)

[REDACTED]

So far, no cases of LON were observed in VAY736 exposed patients after dosing.

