### **Period**

The period 2 starts from the first dose on Day 1 visit; the period 2 end date is the end of treatment date in period 2. The period 3 starts from first dose in period 3; the period 3 end date is defined as the end of treatment date in period 3. The period 4 starts on the day after the end of treatment in period 2/3. Assignment of events to each period will be based on date and time. When time is missing or not reported, the assignment will be based on date only; in that case, events starting on the date of first dose in period 3 will be assigned to the period 3 for those who are entering period 3, or to the safety follow-up period.

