### 5.2.2 AE date imputation

The following missing dates will not be imputed:

- Missing AE start dates
- AE start dates missing the year
- Partial/missing AE end dates

For other type of partial missing start dates, rules specified in the following tables will be used.

	Day	Month	Year
Partial Adverse Event Start Date	Not used	MON	YYYY
Treatment Start Date	Not used	TRTM	TRTY

The following matrix explains the logic behind the imputation.

	MON MISSING	MON < TRTM	MON = TRTM	MON > TRTM
YYYY MISSING	( 1 ) No convention			
YYYY < TRTY	( 2.a ) Before Treatment Start	( 2.b ) Before Treatment Start	( 2.b ) Before Treatment Start	( 2.b ) Before Treatment Start
YYYY = TRTY	( 4.a ) Uncertain	( 4.b ) Before Treatment Start	( 4.c ) Uncertain	( 4.c ) After Treatment Start
YYYY > TRTY	( 3.a ) After Treatment Start	( 3.b ) After Treatment Start	( 3.b ) After Treatment Start	( 3.b ) After Treatment Start

Impute AE start date -

1. If the AE start date year value is missing, the date uncertainty is too high to impute a rational date. Therefore, if the AE year value is missing, the imputed AE start date is set to NULL.
2. If the AE start date year value is less than the treatment start date year value, the AE started before treatment. Therefore:
  - a. If AE month is missing, the imputed AE start date is set to the mid-year point (01JulYYYY).

- b. Else if AE month is not missing, the imputed AE start date is set to the mid-month point (15MONYYYY).
3. If the AE start date year value is greater than the treatment start date year value, the AE started after treatment. Therefore:
  - a. If the AE month is missing, the imputed AE start date is set to the year start point (01JanYYYY).
  - b. Else if the AE month is not missing, the imputed AE start date is set to the later of (month start point (01MONYYYY), treatment start date + 1 day).
4. If the AE start date year value is equal to the treatment start date year value:
  - a. And the AE month is missing the imputed AE start date is set to the treatment start date + 1 day.
  - b. Else if the AE month is less than the treatment start month, the imputed AE start date is set to the mid-month point (15MONYYYY).
  - c. Else if the AE month is equal to the treatment start date month or greater than the treatment start date month, the imputed AE start date is set to the later of (month start point (01MONYYYY), treatment start date + 1 day).

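### SAP 2.1.1 gives two conflicting rules for adverse events on the day of the first period 3 dose; read literally, one counts events after a placebo patient's first VAY736 injection under placebo

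*SAP*

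**What the plan says.** Four parts of SAP 2.1.1 bear on this point.

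- **Study treatment, Grouping Scheme 1 (24-week safety summary).** The data cut is "only data on or before the end of treatment (defined below) in period 2 will be tabulated". The column label is fixed by the starting arm: "The treatment used will be according to the treatment groups initially received".
- **Study treatment, Grouping Scheme 2 (all periods).** Its columns are 5 mg, 50 mg, 150 mg, three 300 mg groups and any VAY736. It has no placebo column.
- **End of Treatment Date.** For period 2: "patients entering period 3: EoT = the date of the first dose in period 3". Patients who finish period 2 and go straight to period 4 use their period 2 disposition date instead.
- **Period.** The end of period 2 is set equal to the period 2 end-of-treatment date, yet "The period 3 starts from first dose in period 3". Events are to be placed by date and time. If the time is missing, "events starting on the date of first dose in period 3 will be assigned to the period 3" for patients who continue.

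SAP 1.1 and Protocol 3.1 move placebo patients to VAY736 150 mg at week 24, without re-randomization.

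**The concern.** The day of the first period 3 dose is the day a placebo patient first receives active drug. A safety cut that includes the whole of that day, with the label still placebo, puts events after the first active injection into the control column.

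The effect runs in one direction: placebo incidence goes up and the difference from VAY736 goes down. First-dose reactions are also what the protocol expects of this drug. Protocol 3.6 says: "First-dose mild-to-moderate injection reactions were observed in the phase 1/2a studies in a substantial subset of patients". Protocol 5.5.4 keeps patients on site for at least 6 hours after the first dose in period 3, so same-day events are likely to be captured.

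The 300 mg column is not affected in the same way. Patients from that arm who continue also have the day included, but they receive either a further 300 mg dose or placebo, not a first active dose. Patients on 5 mg and 50 mg have no period 3 dose. Only Scheme 1 offers a placebo comparison, so no second grouping would correct the contrast.

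**Working it through.** The plan states no figure on this point, so the check sets the two rules side by side and then bounds the size.

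**Step 1: one day, two rules.** Put the first period 3 dose on day 168, the week 24 target day in SAP Table 5-1, for a patient who started on placebo.

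| Event onset | Scheme 1 cut with the end-of-treatment definition | Period paragraph | Agree? |
|---|---|---|---|
| Day 168, timed before the dose | In the placebo column | Period 2 | Yes |
| Day 168, timed after the dose | In the placebo column | Period 3 | No |
| Day 168, no time recorded | In the placebo column | Period 3 | No |
| Day 169 | Outside the cut | Period 3 | Yes |

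The rules conflict in two of the four cases. In the post-dose case the literal cut gives a wrong attribution. In the untimed case it takes the opposite default from the Period paragraph.

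**Step 2: which rule governs.** Scheme 1 points forward to the end-of-treatment definition and to nothing else. The Period paragraph concerns assignment of events to periods and does not mention Scheme 1. No sentence says whether the Scheme 1 cut is made before, after or independently of that assignment.

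**Step 3: how many patients.** Patients affected = n × r.

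- n is the number of placebo patients entering period 3. SAP 1.1 plans about 45 per arm. The documents do not give the share who continue, so 36 to 45 is assumed.
- r is the share with a reaction starting after the dose on that calendar day. The documents give no rate, so 5% to 50% is assumed.

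Literal reading:

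- Lowest: 36 × 0.05 = 1.8
- Middle: 40 × 0.20 = 8.0
- Highest: 45 × 0.50 = 22.5

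This gives about 2 to 22 patients. The count of newly affected patients is lower if some had already reported the same type of event on placebo, because the tables count each patient once.

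If the Period rule governs, the number is 0.

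**The case against.** The strongest reply is that the Period paragraph already deals with this day. It ties the end of period 2 to the end-of-treatment date and then says how events on the shared date are divided. As the more specific rule, it may be what the sponsor means to program, and then no same-day event is misplaced. That stands as a plausible reading. It does not settle the matter, because Scheme 1 selects by an inclusive date and never invokes the period assignment. A programmer who follows the Scheme 1 text would produce the other result.

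Second, injection reactions are also summarized by visit (SAP 2.7.2) and recorded on dedicated forms (Protocol 6.5.7). The first period 2 dose (visit 101) and the first period 3 dose (visit 201) are separate visits, so the by-visit table still shows a clean first-dose comparison. This stands, and it limits how far a reaction signal could be hidden. It does not repair the adverse event tables by organ class and preferred term in SAP 2.7.1, which have no visit breakdown.

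Third, onsets on the next day or later fall outside the cut on either reading. This also stands.

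A reader might also infer that the partial-date rules make things worse, since for an onset month at or after the start of treatment "the imputed AE start date is set to the later of (month start point (01MONYYYY), treatment start date + 1 day". That start is the first dose of all, so a missing-day event in the month of the switch is usually set to the 1st, which is placebo time. The documents do not support a change on this ground. They give no frequency of partial dates, and a missing day is least likely for reactions watched on site. Moving the anchor for placebo patients alone would treat arms differently. It would also often be wrong. With onset uniform over a 30-day month and the dose equally likely on any day, the mean share of onsets on or after the dose is (30 + 29 + … + 1)/(30 × 30) = 465/900 = 0.52, so about 48% of such events truly began before it.

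**Conclusion.** The concern holds as an unreconciled contradiction within SAP 2.1.1. One of the two stated rules puts events after a placebo patient's first VAY736 injection in the only placebo safety column, and the SAP does not say that the other rule overrides it.

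The size cannot be fixed from the documents. It is zero if the Period rule governs, and about 2 to 22 patients under the literal reading with the assumed 36 to 45 continuing placebo patients and 5% to 50% same-day rate.

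It would be tempting to say that these reactions will be reported under placebo, or that the drug-placebo difference will vanish or reverse. The first takes one reading as settled when the text leaves two open. The second needs the literal reading together with reaction rates that appear nowhere in the documents, and it passes over the by-visit summary.

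The schemes govern safety summaries only, so the primary efficacy analysis is untouched. The clarification should still be made, because the possible bias runs in one direction and is cheap to remove.

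**What to change.** Add one sentence to Grouping Scheme 1 in SAP 2.1.1: adverse event and injection-reaction tables include only events assigned to period 2 under the Period paragraph. For patients entering period 3, that means onset before the first period 3 dose, with untimed same-day events going to period 3. Apply it in all arms. State also that week 24 laboratory, vital sign and ECG values taken before that dose remain in Scheme 1, since an inclusive date suits those measurements. Leave the partial-date imputation rules as they are.

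The cost is one sentence and one selection condition in the safety programs, with no new data. The downside is that some untimed same-day events that truly began before the dose will leave the 24-week table. Protocol 7.1 asks for start and end dates of adverse events and does not mention times, so the untimed default may be used often. The loss is still confined to onsets on a single calendar day before the injection, and should be a few events.

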3.1 Study design

This is a randomized, double-blind, placebo-controlled, multicenter, parallel-group trial in approximately 180 patients with active pSS. The study is divided into 4 study periods:

Period 1: A screening period of 4 weeks to assess patient eligibility. Patients can be re-screened only once and no study-related re-screening procedure should be performed prior to written re-consent by the patient.

Period 2: At baseline, eligible patients will be randomized to one of three VAY736 dose arms (VAY736 5 mg, 50 mg or 300 mg s.c.) or a placebo arm. Blinded study drug will be administered every four weeks for a 24-week period. Approximately 45 patients will be randomized per treatment group. [REDACTED], randomization will be stratified by:

- baseline ESSDAI score (<10 or ≥ 10 based on weighted scores)

[REDACTED]

The primary endpoint will be assessed at the end of period 2 (week 24).

[figure not shown]
Treatment assignment in period 2 will remain double blinded until the end of period 3.

Period 3: After week 24 assessments, patients in the VAY736 300 mg arm will be re-randomized in a 1:1 ratio to either continue VAY736 300 mg s.c. every four weeks or switch to [REDACTED] placebo up to week 52. Patients who received placebo during period 2 will be switched to VAY736 150 mg s.c every four weeks up to week 52. Patients who received 5 mg and 50 mg s.c. in period 2 will proceed directly to period 4. Treatment assignment in period 3 will remain double blinded until the end of the study period.

Period 4: The safety follow-up period lasts for a minimum of 20 weeks from last dose administration of VAY736, or longer (with reduced visit frequency) [REDACTED]

[REDACTED] Patients who will be treated with another immunmodulatory or immunsuppressive treatment (e.g. azathioprine, cyclophosphamide, high dose glucocorticosteroids) after completion of the minimum 20 week safety follow-up period are excluded from further safety follow-up.

The primary efficacy analysis will be performed when all patients have completed the week 24 study visit. An interim analysis will occur when approximately 100 patients have completed their Week 24 visit.

Figure 3-1 Study design

*Only patients in the period 2 VAY736 300 mg arm will be eligible for period 3 re-randomization.

[figure not shown]

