If discontinuation of study treatment occurs, the patient should NOT be considered withdrawn from the study. The patient should continue to return to the clinic for the scheduled visits in the respective treatment period. If the patient decides to leave the study, a study treatment discontinuation visit must occur as soon as possible after actual discontinuation of the study drug. Treatment discontinuation visit assessments detailed in the "unscheduled treatment discontinuation visit" (TD) in [Table 6-1](#) and [Table 6-2](#) should be completed and recorded in the eCRF. The investigator must determine the primary reason for the patient's premature discontinuation of study treatment and record this information on the Dosage Administration eCRF.

Patients who discontinue after having received at least one VAY736 administration and who do not complete the visits in the respective treatment period should return for the long-term safety follow up period 4. In period 4, visits are scheduled as outlined in [Table 5-3](#) below

Table 5-3 Outline of visit frequency in period 4

Visit frequency	TD period 2	TD period 3	No. of visits
Every 4 weeks	week 24 -week 40	week 52 - week 68	4 visits
Every 8 weeks	week 40 - week 56	week 68 - week 84	2 visits
Every 12 weeks	week 56 - week 80	week 84 - week 108	2 visits
Every 24 weeks	week 80- week 128	week 108 - week 156	2 visits

TD = Study treatment discontinuation

The End-of-Study visit will include study completion evaluations followed by discharge from the study. Patients who discontinue during the safety follow up period will be asked to complete the end of study visit. For patients who are lost to follow-up (i.e., those patients whose status is unclear because they fail to appear for study visits without stating an intention to withdraw), the investigator should show “due diligence” by documenting in the source documents steps taken to contact the patient, e.g., dates of telephone calls, registered letters, etc.

The investigator must also contact the IRT to register the patient’s discontinuation from study treatment.

If study drug discontinuation occurs because treatment code has been broken, please refer to [Section 5.5.9](#).

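### In the readable SAP, the only safety grouping with a placebo column stops 27 days after the last dose for patients who discontinue early in period 2, so their later events before week 24 enter no placebo-controlled table

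*SAP*

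**What the plan says.** SAP section 2.1.1 (Study treatment) introduces two rules that fix both the columns and the data for safety output: "The following grouping scheme / data selection will be used for reporting of safety summary".

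- Scheme 1 is labelled "Grouping Scheme 1 (short term summary, up to 24 weeks". Its groups are placebo, 5 mg, 50 mg, 300 mg and any VAY736. Its data rule is that "only data on or before the end of treatment (defined below) in period 2 will be tabulated".
- Scheme 2 is labelled "Grouping Scheme 2 (long term summary, all study periods". Its groups are 5 mg, 50 mg, 150 mg, 300 mg for 24 weeks, 300 mg for 52 weeks, any 300 mg and any VAY736. It has no placebo group.

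The end of treatment that closes Scheme 1 depends on how the patient leaves period 2. One rule is "patients who complete period 2 treatment and enter period 4 directly: EoT = the date of period 2 disposition on CRF page". Patients who go on to period 3 are closed at their first period 3 dose. For the rest, the rule is "patients early discontinue the treatment in Period 2: EoT = the date of the last dose in period 2 plus 27 days". The SAP's Period definition then starts period 4 on the following day, with no exception when that day falls before week 24.

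Protocol section 5.6.2 says of a patient who stops treatment: "The patient should continue to return to the clinic for the scheduled visits in the respective treatment period". Protocol section 7.1 collects adverse events to the end-of-study visit. The SAP's definition of a treatment-emergent event has a start condition but no end date.

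**The concern.** A treatment-emergent event on day 60 in a patient whose only dose was on day 1 is collected and meets the SAP's own definition. It still falls outside Scheme 1, because that patient's period 2 closed on day 28. If the patient was on VAY736, the event appears in Scheme 2 with no control beside it. If the patient was on placebo, it appears in neither scheme. Such a patient cannot reach the 150 mg column either, because Protocol section 3.6 bars placebo patients who discontinue before week 24 from active treatment in period 3.

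The patients affected are not a random subset. Protocol section 5.6.2 requires stopping for adverse events or laboratory findings that indicate a safety risk. It also requires stopping to be considered for persistent neutropenia of grade 3 or higher and for serious or severe infection. At stake is whether the report can show a randomised comparison to week 24 of everyone who started treatment. The primary efficacy estimand in SAP section 2.5.1 takes that view, disregarding treatment interruption and early termination. The readable safety plan has no counterpart.

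**Working it through.** The plan states no figure to reproduce. The check is day arithmetic on the SAP's rules.

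**Inputs**
- Period 2 dosing days 1, 28, 56, 84, 112 and 140, and week 24 at day 168 (Protocol Table 6-1; last dose at visit 106, Protocol section 5.5.4).
- End of treatment for early stoppers = last-dose day + 27 (SAP 2.1.1).
- About 45 patients per arm (SAP 1.1).
- Early-stopping rate: not given in the readable text. Assumed 5% to 15%, spread evenly over last doses 1 to 5.

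**Uncovered days before week 24** = 168 − (last-dose day + 27)

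| Last dose received | Dose day | End of treatment | Days outside Scheme 1 | Share of 168 days |
|---|---|---|---|---|
| 1 | 1 | 28 | 140 | 83% |
| 2 | 28 | 55 | 113 | 67% |
| 3 | 56 | 83 | 85 | 51% |
| 4 | 84 | 111 | 57 | 34% |
| 5 | 112 | 139 | 29 | 17% |
| 6 | 140 | 167 | 1 | 0.6% |

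The last row is a consistency check. After all six doses the 27-day rule lands one day short of week 24, so it removes material time only from early stoppers.

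**Share of controlled person-time**
- Mean loss per stopper: (140 + 113 + 85 + 57 + 29) / 5 = 84.8 days, and 84.8 / 168 = 50.5%.
- At 5% stopping: 0.05 × 50.5% = 2.5%. Per arm, 45 × 0.05 = 2.25 patients and 2.25 × 84.8 = 191 of 45 × 168 = 7,560 patient-days.
- At 15% stopping: 0.15 × 50.5% = 7.6%. Per arm, 45 × 0.15 = 6.75 patients and 6.75 × 84.8 = 572 patient-days.

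**Where an event between end of treatment and week 24 is reported**

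| Patient stopped | Scheme 1 (has placebo) | Scheme 2 (no placebo) |
|---|---|---|
| VAY736 | No | Yes, uncontrolled |
| Placebo | No | No |

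**A related point on rates.** The exposure-adjusted event rate in SAP section 2.7.1 divides by time to the study cutoff or end of study, whichever is earlier. The SAP does not say whether this denominator is used with Scheme 1. If it is, events stop at end of treatment while time at risk continues, and the rate is biased downward.

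**The case against.** The strongest reply is that Scheme 1 is a coherent on-treatment summary. The last-dose day plus 27 more days is one four-week dosing interval, the same coverage a completer gets after the day 140 dose. Events after stopping may also reflect other drugs: Protocol Table 5-2 names prohibited therapies that lead to stopping while the patient stays in the study. The cut applies to every arm, the lost share is small, and the toxicity that prompts stopping will usually have begun before the cut and so be counted. All of this stands. It is a reason to keep Scheme 1, but not a reason to have no companion table.

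A reader might infer more than the documents support, in four ways:

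- **That these events never meet a controlled comparison.** The DMC reviews cumulative unblinded safety data (Protocol section 8.4), parts of the SAP are redacted, and compound-specific risks follow documents not available here (SAP section 2.7.1). The supportable statement concerns the groupings in the readable SAP.
- **That the active–placebo difference is understated.** This would need more stopping followed by later events on VAY736 than on placebo. No document gives stopping rates or reasons by arm, and patients also stop by choice, for pregnancy or after a live vaccine.
- **That the follow-up rule ("The safety follow-up period lasts for a minimum of 20 weeks from last dose administration of VAY736") or late-onset neutropenia shows 27 days to be too short.** That argument applies equally to completers, and a table ending at week 24 would not answer it. The readable text of Protocol section 3.6 also reports no cases of late-onset neutropenia so far.
- **That every stopper has scheduled data to week 24.** Section 5.6.2 keeps stoppers on the treatment-period visits, but note 7 to Table 6-1 sends them into period 4 after the discontinuation visit. Adverse events are collected under either reading. Scheduled laboratory data at the period 2 visits cannot be assumed for all.

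**Conclusion.** The point holds as a gap in the planned safety tables. In the readable SAP, no placebo-controlled summary covers early stoppers from 28 days after their last dose to week 24, and placebo stoppers' events in that window fall under neither scheme. The label on Scheme 1 does not close the gap, because its data rule cuts at end of treatment and not at week 24. Protocol section 9.5.2 summarises treatment-emergent events by treatment without mentioning such a cut, and SAP section 4 records no change from the protocol.

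The day counts per stopper (140 down to 29) follow from the SAP's rules and the nominal visit days. The overall 2.5% to 7.6% rests on the assumed 5% to 15% stopping rate and the even spread over doses 1 to 5. The loss is modest in total but falls entirely on patients who stopped, in arms of about 45. The direction of any bias is not known, and the primary efficacy analysis is untouched. This is an inexpensive improvement worth making, not evidence that the safety comparison is wrong.

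**What to change.** 1. Keep Scheme 1 and label it as the on-treatment summary.
2. Add a companion set with the same columns, including placebo, for treatment-emergent events, serious events, infections and neutropenia. Count all events from first dose to week 24 (day 168, or the first period 3 dose), whether or not treatment was stopped.
3. Compute exposure-adjusted rates in each set with person-time over the same window as the events counted. For the companion set, that means time to week 24, the first period 3 dose or study exit, whichever comes first.
4. Reconcile Protocol section 5.6.2 with note 7 to Table 6-1 on which visits early stoppers attend, so that it is clear what data the companion set can use.

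The cost is one further set of safety tables from data the protocol already collects, with no change to the design or to the primary analysis. The drawback is that the added tables include events after treatment was stopped, possibly under other therapies, so they should be read beside the on-treatment set.
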